## 4.3. Exploratory Objectives

The exploratory objectives of this study are as follows:

Objectives/Endpoints

Exploratory Endpoints may include evaluating the response to baricitinib treatment regimens on clinical measures and patient-reported outcomes. These endpoints may include dichotomous endpoints or change from baseline for the following measures: IGA, EASI, SCORAD, POEM, DLQI, WPAI-AD, EQ-5D-5L, Itch NRS, ADSS Item 1, 2, and 3 scores, Skin Pain NRS, SF-36, and PGI-S-AD. Patients continuing on placebo as responders will be assessed during the Long-Term Extension for relevant efficacy endpoints.

Prior to the WK104 DBL, exploratory analysis endpoints include:

EASI at Week 16:
 
 
• Proportion of patients achieving EASI <math>\leq 7</math>
 
• Change from baseline in EASI total score
 

EASI at Week 52:
 
 
• Proportion of patients achieving EASI50
 
• Proportion of patients achieving EASI90
 
• Change and percent change from baseline in EASI total score
 
• Proportion of patients achieving EASI <math>\leq 7</math>
 

Proportions of patients achieving IGA of 0 or 1 or 2 at Week 52

SCORAD at Week 16:
 
 
• Proportion of patients achieving SCORAD <math>\leq 25</math> (in the subset of patients with SCORAD <math>>25</math> at baseline)
 
• Percent change from baseline in SCORAD
 

SCORAD at Week 52:
 
 
• Proportion of patients achieving SCORAD75
 
• Mean change and percent change from baseline in SCORAD
 
• Proportion of patients achieving SCORAD <math>\leq 25</math> (in the subset of patients with SCORAD <math>>25</math> at baseline)
 

To evaluate the effect of maintaining baricitinib effect on key clinical measures:
 
 
• Proportion of IGA (0,1) responders at Week 24 for those patients with an IGA (0,1) response at Week 16
 
• Proportion of EASI75 responders at Week 24 for those patients with an EASI75 response at Week 24
 

Time to event analysis:
 
 
• Time to first EASI75 reduction response
 
• Time to first IGA (0,1) response
 
• Time to first Itch NRS 4-point improvement response
 

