**For Week-104 DBL and Final DBL, exploratory analysis endpoints include:**

EASI at Week 68, Week 104 and Final DBL:

- Proportion of patients achieving EASI50
- Proportion of patients achieving EASI90
- Change and percent change from baseline in EASI total score

- Proportion of patients achieving EASI  $\leq 7$

Itch NRS at Week 68:

- Proportion of patients achieving a 4-point improvement in Itch NRS
- Change and percent change from Baseline in Itch NRS score

DLQI at Week 68, Week 104 and Final DBL:

- Proportion of patients achieving a DLQI total score of 0 or 1
- Proportion of patients achieving a DLQI total score of 5 or less for those with a baseline DLQI total score  $> 5$
- Mean change from baseline in DLQI total score

ADSS at Week 68:

- Mean change from baseline in ADSS Item (1, 2, 3) score at Week 68 and Week 104
- Proportion of patients achieving a  $\geq 1.5$ -point improvement in ADSS Item 2 score for those with a baseline Item 2 score  $\geq 1.5$

Skin Pain NRS at Week 68:

- Mean change from baseline in Skin Pain NRS
- Proportion of patients achieving a  $\geq 4$ -point improvement

Patient Global Impression of Severity PGI-S-AD at Week 68:

- Mean change from baseline in PGI-S-AD

Time to Relapse (IGA  $\geq 3$ )

- Kaplan-Meier plot

Abbreviations: ADSS = Atopic Dermatitis Sleep Scale; DBL = database lock; DLQI = Dermatology Life Quality Index; EASI = Eczema Area and Severity Index; EASI75 = 75% improvement from baseline in Eczema Area and Severity Index score; EQ-5D-5L = the European Quality of Life-5 Dimensions 5 Levels; HADS = Hospital Anxiety Depression Scale; IGA = Investigator's Global Assessment for AD; NRS = Numeric Rating Scale; PGI-S-AD = Patient Global Impression of Severity-Atopic Dermatitis; POEM = Patient-Oriented Eczema Measure; SF-36 = Medical Outcomes Study 36-item short-form health survey; SCORAD = Scoring Atopic Dermatitis; WPAI-AD = Work Productivity and Activity Impairment-Atopic Dermatitis.

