#### *Period 3 and Period 4 (Study Weeks 52 to 200)*

For analysis of endpoints assessed at scheduled visits in Periods 3 and 4, baseline from Week 0 will be used for categorical endpoints, such as EASI75, Itch NRS  $\geq 4$ -point improvement response, etc. Baseline from Week 0 will also be used for EASI-related, continuous endpoints, such as EASI change or percent change from baseline. For the other continuous endpoints such as Itch NRS and Dermatology Life Quality Index (DLQI) change from baseline, the analysis will be done using the Week 52 baseline. The methodology for defining Week 52 as the baseline is the same as the methodology for defining Week 0 of the originating study described above, anchoring on the first study drug administration of Period 3. See [Table JAIN.6.9](#) and [Table JAIN.6.12](#) for a detailed descriptions on endpoint derivation and associated baseline definition.

Baseline daily-diary definition will be same to the Period 2's definition for daily-diary data.

Postbaseline measurements are collected after study drug administration through Week 200 (Visit 28) or early discontinuation visit. Data collected on scheduled visits will generally be used for efficacy and health outcome analyses. If data for a scheduled visit are missing, data from the most proximal unscheduled visits, if available, will be used if it falls within visit windows as follows: a 2-day interval around the scheduled visit day (4-day window) is applied to Visits 3 to 6 (Week 1, 2, 4, 8), a 4-day interval around the scheduled visit day (8-day window) is applied to Visits 7 to 9 (Week 12, 16, 20), a 5-day interval around the scheduled visit day (10-day window) is applied to Visits 10 to 14 (Week 24, 32, 40, 48, 52), a 4-day interval around the scheduled visit day (8-day window) is applied to Visits 15 to 18 (Week 56, 60, 64, 68), a 5-day interval around the scheduled visit day (10-day window) is applied to Visits 19 to 22 (Week 76, 84, 92, 104), and a 7-day interval around the scheduled visit day (14-day window) is applied to

Visits 23 to 28 (Week 120, 136, 152, 168, 184, and 200). If there is more than 1 unscheduled visit within the defined visit window and no scheduled visit is available, the unscheduled visit closest to the scheduled visit date will be used. If only 2 equal distance unscheduled visits are available, the later of the 2 visits will be used.

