	DLQI total score of 0 to 1 is considered as having no effect on a patient's health-related QoL (Hongbo et al. 2005), and a 4-point change from baseline is considered as the minimal clinically important difference threshold (Khilji et al. 2002; Basra et al. 2015).	
 
Personal relationships domain
 
Treatment domain
 
DLQI total score
 
Change from baseline in DLQI
 
DLQI total score <math>\leq 5</math> in subgroup of patients who had baseline DLQI <math>>5</math>
 
DLQI total score in (0,1)
 
4-point DLQI improvement in subgroup of patients with baseline DLQI total score <math>\geq 4</math>
 
	
Sum of questions 8 and 9, range 0 to 6.
 
Question 10, range 0 to 3.
 
DLQI total score: sum of all 6 DLQI domain scores, range 0 to 30.
 
Change from baseline: observed DLQI score – baseline DLQI score
 
Post-baseline DLQI total score <math>\leq 5</math> with baseline total score <math>>5</math>
 
Post-baseline DLQI total score in (0,1)
 
Change from baseline <math>\leq -4</math> and baseline <math>\geq 4</math>
	
N/A – partial assessments cannot be saved.
 
N/A – partial assessments cannot be saved.
 
N/A – partial assessments cannot be saved.
 
Missing if baseline or observed value is missing.
 
Missing if baseline is missing or <math>\leq 5</math> or observed value is missing.
 
N/A – partial assessments cannot be saved.
 
Missing if baseline is missing or <math>< 4</math> or observed value is missing.

Measure	Description	Variable	Derivation / Comment	Imputation Approach if with Missing Components

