**Table JAIN.6.12. Description of Health Outcomes and Quality-of-Life Measures Analyses (Period 3 and Period 4)**

Measure	Variable	Population (Section 6.2.1)	Analysis Method (Section 6.2.2)	Time Point	Baseline Definition
Itch Numeric Rating Scale (NRS)	Itch NRS score	LTE Substudy Population	Descriptive using Obs and mLOCF	Weeks 52-68	Week 52 Baseline
	Change from baseline in Itch NRS score	LTE Substudy Population - Patients with IGA of 0 or 1 at Week 52	Descriptive using Obs and mLOCF	Weeks 52-68	Week 52 Baseline
	Percent change from baseline in Itch NRS score	LTE Non-responder Population	Descriptive using Obs and mLOCF	Weeks 52-68	Week 52 Baseline
		LTE Responders & Partial Responders who did not enter the study	Descriptive using Obs and mLOCF	Weeks 52-68	Week 0 Baseline
	Proportion of patients with a 4-point improvement from baseline of originating study in Itch NRS in subgroup of patients who had baseline Itch NRS $\geq 4$	LTE Substudy Population	Descriptive using Obs and mLOCF	Weeks 52-68	Week 0 Baseline
		LTE Substudy Population – Patients with IGA of 0 or 1 at Week 52	Descriptive using Obs and mLOCF	Weeks 52-68	Week 0 Baseline
		LTE Non-responder Population	Descriptive using Obs and mLOCF	Weeks 52-68	Week 0 Baseline
		LTE Responders & Partial Responders who did not enter the study	Descriptive using Obs and mLOCF	Weeks 52-68	Week 0 Baseline
	Skin Pain NRS	LTE Substudy Population	Descriptive using Obs and mLOCF	Weeks 52-68	Week 52 Baseline
	Change from baseline in Skin Pain NRS score				

Measure	Variable	Population (Section 6.2.1)	Analysis Method (Section 6.2.2)	Time Point	Baseline Definition
Skin Pain NRS	Skin Pain NRS score Change from baseline in Skin Pain NRS score	LTE Substudy Population with Week 52 IGA of 0 or 1	Descriptive using Obs and mLOCF	Weeks 52-68	Week 52 Baseline
		LTE Non-responder Population	Descriptive using Obs and mLOCF	Weeks 52-68	Week 52 Baseline
	Proportion of patients with a 4-point improvement from baseline of originating study in Skin Pain in subgroup of patients who had baseline Skin Pain NRS $\geq 4$	LTE Responders & Partial Responders who did not enter the study	Descriptive using Obs and mLOCF	Weeks 52-68	Week 0 Baseline
		LTE Substudy Population	Descriptive using Obs and mLOCF	Weeks 52-68	Week 0 Baseline
		LTE Substudy Population - Patients with IGA of 0 or 1 at Week 52	Descriptive using Obs and mLOCF	Weeks 52-68	Week 0 Baseline
		LTE Non-responder Population	Descriptive using Obs and mLOCF	Weeks 52-68	Week 0 Baseline

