		LTE Responders & Partial Responders who did not enter the Substudy	Descriptive using Obs and mLOCF	Weeks 52-200	Week 0 Baseline
	Proportion of patients with DLQI (0, 1)	LTE Substudy Population	Descriptive using Obs and mLOCF	Weeks 52-200	DLQI (0,1) N.A. DLQI $\leq 5$ uses Week 0 Baseline
	Proportion of patients with DLQI Total Score	LTE Substudy Population - Patients with IGA of 0 or 1 at Week 52	Descriptive using Obs and mLOCF	Weeks 52-200	DLQI (0,1) N.A. DLQI $\leq 5$ uses Week 0 Baseline

	5 or less with baseline >=4	LTE Non-responder Population	Descriptive using Obs and mLOCF	Weeks 52-200	DLQI (0,1) N.A. DLQI <=5 uses Week 0 Baseline
		LTE Responders & Partial Responders who did not enter the Substudy	Descriptive using Obs and mLOCF	Weeks 52-200	DLQI (0,1) N.A. DLQI <=5 uses Week 0 Baseline

Abbreviations: ADSS = Atopic Dermatitis Sleep Scale; DLQI = Dermatology Life Quality Index; IGA = Investigator's Global Assessment for AD; LTE = Long-Term Extension; ; mLOCF = modified last observation carried forward; NRS = Numeric Rating Scale; Obs = Observed; PGI-S-AD = Patient Global Impression of Severity-Atopic Dermatitis.

Notes: missing data related to COVID-19 may be imputed using the method specified in Section [6.3.7](#).

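### Three exploratory rules in the SAP need correction or reconciliation: EASI75 maintenance is conditioned on its own visit, Table JAIN.6.12 uses a different DLQI subset, and baselines conflict in Periods 3 and 4

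*SAP*

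**What the plan says.** **EASI75 maintenance.** SAP Section 4.3 has a pair of endpoints introduced by "To evaluate the effect of maintaining baricitinib effect on key clinical measures". The first is "Proportion of IGA (0,1) responders at Week 24 for those patients with an IGA (0,1) response at Week 16". The second is "Proportion of EASI75 responders at Week 24 for those patients with an EASI75 response at Week 24".

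**DLQI ≤5.** For the Week 104 and final locks, Section 4.3 lists "Proportion of patients achieving a DLQI total score of 5 or less for those with a baseline DLQI total score" above 5. Table JAIN.6.10 derives the variable "in subgroup of patients who had baseline DLQI" above 5 and sets it to missing when baseline is 5 or lower. Table JAIN.6.11 also uses >5, for Week 16. Table JAIN.6.12, which governs Periods 3 and 4, instead has a total score of "5 or less with baseline >=4", with Week 0 as the baseline.

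**Baseline in Periods 3 and 4.** Section 6.2.2.1 keeps the Week 0 baseline for categorical and EASI-related endpoints. For other continuous endpoints, with Itch NRS and DLQI as examples, it says "the analysis will be done using the Week 52 baseline". It names no exception by population, and it sends the reader to Tables JAIN.6.9 and JAIN.6.12 for endpoint and baseline detail. Table JAIN.6.12 gives Week 52 for the substudy population, its IGA 0/1 subset and the non-responders. For the fourth population it gives Week 0. That population is labelled "Partial Responders who did not enter the study" in the diary-measure rows and, in the DLQI rows, as those outside the substudy. The split applies to change in Itch NRS, Skin Pain NRS, ADSS, PGI-S-AD and DLQI.

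**The concern.** An endpoint meant to show whether response persists must condition on an earlier visit than the one at which it is assessed. Conditioning on the same visit leaves nothing to estimate and no contrast between arms.

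A responder definition should exclude patients who already meet the target at entry. Three places in the SAP do this for DLQI ≤5 and one does not, so two programmers following different tables would use different denominators.

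Change scores shown side by side should share an origin, or the table should say that they do not. A reader of Table JAIN.6.12 could take a gap between substudy and non-substudy responders for a clinical difference when it comes only from the choice of baseline.

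**Working it through.** The plan states no numerical result for any of these endpoints, so there is no figure to reproduce. The check is logical, with illustrations on assumed inputs.

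**1. EASI75 maintenance**

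- Let R16 and R24 denote EASI75 response at Weeks 16 and 24. As written, the endpoint is P(R24 | R24) = 1 whenever an arm has at least one Week 24 responder, and is undefined otherwise. This takes the same censoring and nonresponder imputation rule in numerator and denominator; the endpoint line specifies no difference.
- Conditioned as the IGA line is, the endpoint is P(R24 | R16). The documents give no persistence rate. In a simulation with assumed persistence of 50%, 70% and 90%, that form returned 50.1%, 69.7% and 90.0%. The wording as printed returned 100% each time.
- Table JAIN.6.8 has no row for this endpoint. Sections 6.10.3 and 6.17 send untabulated exploratory details to a supplementary SAP or list of analyses. Section 4.3 is therefore the only definition in the documents reviewed.

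**2. DLQI ≤5**

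- DLQI totals are integers from 0 to 30. The rule ≥4 admits 4 to 30; the rule >5 admits 6 to 30. The difference is the values 4 and 5, both already at or below the target.
- Let s be the share of the ≥4 subset with baseline 4 or 5, q the proportion of those who are ≤5 at follow-up, and p the response rate in patients with baseline >5. The reported rate is (1 − s)p + sq, so the distortion is s(q − p).
- None of s, p or q is in the documents. Assuming p = 40%:

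| s | q = 90% | q = 100% |
|---|---|---|
| 2% | 0.98 × 0.40 + 0.02 × 0.90 = 41.0% | 0.392 + 0.02 = 41.2% |
| 5% | 0.38 + 0.045 = 42.5% | 0.38 + 0.05 = 43.0% |
| 10% | 0.36 + 0.09 = 45.0% | 0.36 + 0.10 = 46.0% |
| 15% | 0.34 + 0.135 = 47.5% | 0.34 + 0.15 = 49.0% |

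These values show only how the distortion behaves. They do not estimate what happened in this trial.

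**3. Baseline for change scores**

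| Population in Table JAIN.6.12 | Section 6.2.2.1 | Table JAIN.6.12 |
|---|---|---|
| Substudy | Week 52 | Week 52 |
| Substudy, IGA 0/1 at Week 52 | Week 52 | Week 52 |
| Non-responders | Week 52 | Week 52 |
| Responders and partial responders outside the substudy | Week 52 | Week 0 |

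- A hypothetical patient with DLQI 14 at Week 0, 4 at Week 52 and 4 afterwards has a change of 4 − 4 = 0 in a substudy row and 4 − 14 = −10 in a non-substudy row.
- A hypothetical patient with Itch NRS 7 at Week 0, 3 at Week 52 and 3 at Week 68 shows 3 − 3 = 0 or 3 − 7 = −4.

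**The case against.** **EASI75.** The defence is that this is a typing slip: the introductory line and the IGA endpoint make Week 16 the evident intent, and the programming may have followed a supplementary list that is not available here. That is plausible. A reader might infer that the 24-week analysis reported 100% in every arm, but the documents show only the definition, not an output. What stands is that the SAP's only definition is uninformative and should be corrected.

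**DLQI.** Section 6.11 assigns derivations to Table JAIN.6.10. If that derivation governs, patients at 4 or 5 are missing and are not counted as responders. A reader might infer that non-improvers are necessarily counted, or that reported rates are inflated by a few percentage points. Neither follows: the first depends on which table was followed, and the second rests wholly on assumed inputs. The conflict between the tables stands. The ≥4 threshold belongs to the separate 4-point improvement endpoint, which suggests a copying error but does not prove one.

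**Baseline.** This is where the defence is strongest. Section 6.2.2.1 defers to Table JAIN.6.12 for the associated baseline, and the table labels every row. The Week 0 population continues its original treatment and is censored at dose change, so change from Week 0 is a coherent long-term measure. A reader might infer that Week 52 must be imposed on all four populations; the documents do not require that. Two things still count against the current text. No rationale is given, and staying on treatment does not explain the split, because 4-mg non-responders and substudy patients re-randomized to their existing dose also continue unchanged yet use Week 52.

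It is also fair that no contrast between these populations is planned, that such a contrast would not be randomized, and that absolute scores are listed beside the change scores for the four diary measures. The risk is misreading, not a wrong test.

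**Conclusion.** Items 1 and 2 are wrong as written; item 3 is an unexplained conflict to be reconciled.

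- **EASI75 maintenance:** 100% by construction in any arm with a Week 24 responder, given a common censoring and imputation rule. It carries no information on persistence.
- **DLQI ≤5:** the error is confined to Table JAIN.6.12; the rule in Section 4.3 is sound. If Table JAIN.6.12 was followed, patients at 4 or 5 at Week 0 can count as responders without improving. The size is unknown because the share at 4 or 5 is not given.
- **Baseline:** one of four populations departs from the stated rule on five instruments. Its change scores are not comparable with those in the other rows.

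A reader might infer from errors in endpoint definitions that the main efficacy conclusions are in doubt. They are not. All three items are exploratory and outside the multiplicity scheme in Section 6.4, and Section 6.2.2.3 limits Periods 3 and 4 to descriptive statistics without tests. No primary or key secondary result is affected. The point is minor, but the corrections are easy.

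**What to change.** 1. **Section 4.3.** Change the conditioning visit for EASI75 maintenance to Week 16, to match the IGA line. Because Section 6.16 records the 24-week interim as already conducted, check which denominator was programmed, and rerun only if it was Week 24.
2. **Table JAIN.6.12.** Restrict DLQI ≤5 to patients with Week 0 DLQI >5, as in Section 4.3 and Table JAIN.6.10. Check the program and rerun the descriptive rows if ≥4 was used.
3. **Section 6.2.2.1 and Table JAIN.6.12.** Reconcile the baselines in one of two ways. Either use one baseline for continuous patient-reported measures in all four populations, or write the Week 0 exception into Section 6.2.2.1 with its reason and footnote the table that change scores are not comparable across populations.

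The cost is a few words in the SAP and, where programs followed the wrong text, reruns of exploratory tables. No new data are needed.

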**For Week-104 DBL and Final DBL, exploratory analysis endpoints include:**

EASI at Week 68, Week 104 and Final DBL:

- Proportion of patients achieving EASI50
- Proportion of patients achieving EASI90
- Change and percent change from baseline in EASI total score

- Proportion of patients achieving EASI  $\leq 7$

Itch NRS at Week 68:

- Proportion of patients achieving a 4-point improvement in Itch NRS
- Change and percent change from Baseline in Itch NRS score

DLQI at Week 68, Week 104 and Final DBL:

- Proportion of patients achieving a DLQI total score of 0 or 1
- Proportion of patients achieving a DLQI total score of 5 or less for those with a baseline DLQI total score  $> 5$
- Mean change from baseline in DLQI total score

ADSS at Week 68:

- Mean change from baseline in ADSS Item (1, 2, 3) score at Week 68 and Week 104
- Proportion of patients achieving a  $\geq 1.5$ -point improvement in ADSS Item 2 score for those with a baseline Item 2 score  $\geq 1.5$

Skin Pain NRS at Week 68:

- Mean change from baseline in Skin Pain NRS
- Proportion of patients achieving a  $\geq 4$ -point improvement

Patient Global Impression of Severity PGI-S-AD at Week 68:

- Mean change from baseline in PGI-S-AD

Time to Relapse (IGA  $\geq 3$ )

- Kaplan-Meier plot

Abbreviations: ADSS = Atopic Dermatitis Sleep Scale; DBL = database lock; DLQI = Dermatology Life Quality Index; EASI = Eczema Area and Severity Index; EASI75 = 75% improvement from baseline in Eczema Area and Severity Index score; EQ-5D-5L = the European Quality of Life-5 Dimensions 5 Levels; HADS = Hospital Anxiety Depression Scale; IGA = Investigator's Global Assessment for AD; NRS = Numeric Rating Scale; PGI-S-AD = Patient Global Impression of Severity-Atopic Dermatitis; POEM = Patient-Oriented Eczema Measure; SF-36 = Medical Outcomes Study 36-item short-form health survey; SCORAD = Scoring Atopic Dermatitis; WPAI-AD = Work Productivity and Activity Impairment-Atopic Dermatitis.

## 5. Study Design

Study I4V-MC-JAIN (JAIN) is a Phase 3, multicenter, double-blind, randomized, placebo-controlled study evaluating the safety and efficacy of baricitinib 1-mg QD, 2-mg QD, and 4-mg QD compared with placebo in patients with moderate-to-severe AD who are receiving background topical TCS treatment and who have experienced failure to cyclosporine or are intolerant to, or have a contraindication to, cyclosporine.

The study consists of 5 periods:

**Period 1: Screening Period (Visit 1):** Up to 5 weeks prior to randomization

**Period 2: 52-week Double-Blind Treatment Period:** From Week 0 (Baseline; Visit 2) up to Week 52 (Visit 14)

**Period 3: 52-week Double-Blind, Long-Term Extension Period:** From Week 52 (Visit 14) to Week 104 (Visit 22)

a. Randomized Down-Titration Substudy (Week 52)

Responders (Investigator's Global Assessment for AD [IGA] 0 or 1) and Partial responders (IGA 2) at Week 52 who are eligible to enter the substudy will be rerandomized as follows:

- baricitinib 4-mg treatment group 1:1 to baricitinib 2-mg, or baricitinib 4-mg.
- baricitinib 2-mg treatment group 1:1 to baricitinib 1-mg, or baricitinib 2-mg.

b. Responders (IGA 0 or 1) and Partial responders (IGA 2) at Week 52 who are not eligible to enter the randomized down-titration substudy will continue on the treatment regimen assigned at baseline. However, patients in the placebo, baricitinib 2-mg, and baricitinib 1-mg treatment groups will be automatically rerandomized to either 4-mg or 2-mg baricitinib (1:1) in case of a worsening of symptoms during Period 3, such that IGA increases to  $\geq 3$ . Patients in the baricitinib 4-mg group will remain on 4-mg.

c. Nonresponders (IGA 3 or 4) at Week 52 in the placebo, baricitinib 2-mg, or baricitinib 1-mg treatment groups will be rerandomized at a 1:1 ratio to baricitinib 4-mg or baricitinib 2-mg QD at Week 52. After re-randomization, patients will remain on the same dose of baricitinib for the remainder of the study.

Nonresponders who were randomized to baricitinib 4-mg will remain on 4-mg.

**Period 4: Bridging Extension Period:** From Week 104 (Visit 22) up to Week 200

Patients who have completed Week 104 and have not met criteria for permanent discontinuation will have the possibility to remain in the trial for up to 96 additional weeks (up to Week 200). During Period 4, patients will continue to receive the same treatment (baricitinib or placebo) they received during Period 3, and will have the same options for dose changes as Period 3 (if not already implemented in Period 3):

[figure not shown]
- Randomized Down titration substudy: the substudy will continue during Period 4. Therefore, patients who have not met the criterion for retreatment in Period 3 will have the possibility to be retreated with the baricitinib dose they received prior to the substudy if worsening of AD symptoms occurs such that IGA increases to  $\geq 3$ .
- Patients with an IGA 0, 1, or 2 at Week 52 and who were not eligible to the randomized downtitration, will be rerandomized at a 1:1 ratio to baricitinib 2-mg QD or baricitinib 4-mg QD if they experience a worsening of symptoms of AD such that IGA increases to  $\geq 3$ , unless the randomized uptitration has already occurred in Period 3. Patients in the baricitinib 4-mg group will remain on 4-mg.

**Period 5: Post-Treatment Follow-Up Period:** From last treatment period visit or early termination visit (ETV) to 4 weeks after the last dose of investigational product.

**Treatment Arms and Duration:** At baseline, patients will be randomized at a 1:1:2:1 ratio to receive placebo QD, baricitinib 1-mg QD, baricitinib 2-mg QD, or baricitinib 4-mg QD for up to 104 weeks.

**Number of Patients:** Planned enrollment is 500 patients  $\geq 18$  years of age.

Figure [JAIN.5.1](#) illustrates the study design.

Abbreviations: AD = atopic dermatitis; eGFR = estimated glomerular filtration rate; ET = early termination; IGA = Investigator's Global Assessment; IP = investigational product; PPD = purified protein derivative; QD = once daily; TB = tuberculosis; TCS = topical corticosteroids; V = visit; W = week.

a Applicable to patients taking topical treatments (excluding emollients) or systemic treatments for AD at the time of screening.

b Maximum dose of baricitinib for patients with renal impairment (defined as eGFR <60 mL/min/1.73 m^2) will be 2-mg QD.

c Patients for whom PPD skin test for the evaluation of TB infection was performed at V1 must return and PPD test must be read 48 to 72 hours after Visit 1 (post-PPD).

d At Visit 2 (W0) and up to Visit 22 (W104), patients will be supplied with mild- and moderate-potency TCS to be applied per the guidelines in Section 7.7.2 in the study protocol.

e At Week 52, responders (IGA 0 or 1) and partial responders (IGA 2) who were assigned to baricitinib 4-mg or 2-mg, at randomization, are currently receiving investigational product (does not currently have study drug interrupted), and have not used high- or ultra-high-potency TCS in the previous 14 days will be enrolled into the downtitration substudy. If a patient in the substudy has an IGA ≥3 during Periods 3 or 4, they will be retreated automatically with their presubstudy baricitinib dose for the remainder of the study.

f At Week 52, responders (IGA 0 or 1) and partial responders (IGA 2) in the baricitinib 4-mg or baricitinib 2-mg treatment groups who are not eligible for the randomized downtitration substudy and those who are in the baricitinib 1-mg or placebo groups will remain on their current dose of investigational product. If worsening of AD symptoms occurs any time during Periods 3 or 4 such that a patient's IGA is  $\geq 3$ , with the exception of patients in the baricitinib 4-mg group, they will be rerandomized automatically at a 1:1 ratio to baricitinib 2-mg QD or baricitinib 4-mg QD. Rerandomization will only occur once. Patients in the baricitinib 4-mg group will remain on 4-mg.

g Beginning at Visit 14 (Week 52), nonresponders (IGA  $\geq 3$ ) in the placebo, baricitinib 1-mg or baricitinib 2-mg treatment groups will be rerandomized at a 1:1 ratio to baricitinib 4-mg or baricitinib 2-mg QD. Nonresponders randomized to baricitinib 4-mg at baseline will remain on 4-mg. After rerandomization, patients will remain on the same dose of baricitinib for the remainder of the study.

h Occurs approximately 28 days after the last dose of IP. Not required for patients who have been off drug for 28 days or more at the time of their last visit.

